6.4.2 LIGHT TREATMENT PROCEDURE

Seventeen (17) to 24 days after surgery, the subject will return for the Postop Week 3 evaluation and a 1st adjustment treatment of the RxSight LAL. Subsequent second and third adjustment treatments, if necessary, will all be separated by 3-7 days. The subject will receive the 1st lock-in treatment 3-7 days after the final adjustment treatment. If necessary, lock-in #2 may be performed 3-7 days after lock-in #1. Depending on the adjustment(s) performed, subjects will receive one to three adjustments and one or two lock-in treatments.

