6.4.2.3 Procedure Preparation

Protocol-required measurements should be completed prior to adjustment or lock-in treatments.

The subject should be prepared for light treatments as follows:

Once adequate pupil dilation is achieved, patch the subject's fellow eye and position the subject comfortably in front of the LDD with chin in the chinrest and forehead against the support bar. Ask the subject to grasp the handles on the LDD table for support. Inform the subject to concentrate on the green fixation light presented in front of them and to try and minimize eye movement.

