6.7 CLINICAL PARAMETERS

The following study parameters will be assessed as specified in Table 1 for the RxSight LAL and Table 2 for the Control IOL. Assessments will be performed using the techniques described in and in the order presented here and in Table 1.

- 1. Demographics
- 2. Daily Life Erythropsia Questionnaire (DLEQ) (RxSight LAL only)
- 3. Ocular history
- 4. History of Medications
- 5. Corneal Keratometry
- 6. Specular Microscopy (substudy)
- 7. Uncorrected distance visual acuity (UCDVA)
- 8. Manifest Refraction
- 9. Best corrected distance visual acuity (BCDVA)
- 10. In-office Erythropsia Assessment (RxSight LAL only)
- 11. City University Color Test (RxSight LAL only)
- 12
- 13. Intraocular pressure
- 14. Slit Lamp Examination
- 15. Fundus Exam
- 16. Fundus Photos
- 18. Dilated pupil diameter
- 20. Adverse Events

Table 1. RxSight LAL Schedule of Visits and Clinical Parameters

Table 1. RxSight LAL Schedule of Visits and Clinical Parameters													
Visits	Preop	Орегайче	Postop Day 1	Postop Week 1	Postop Week 3	Adjustment #2 (If needed)	Adjustment #3 (if needed)	Lock-in #1	Lock-in#2 (if nædeil)	Postop Months 1-2	Postop Mouth 6	Postop Month 12 (if needed)	Unscheduled Visit
Demographics	Х												
Daily Life Brythropsia Questionnaire (DLEQ)					х	X	х	х	х	X ⁴	х	Х	X
Ocular History	х												
History of Medications	Х	Х	X	Х	х	X.	х	Х	х	X	х	X	Х
Corneal Keratometry	х												
Specular Microscopy ³	Х				х						x		
Uncorrected distance visual actity (UCDVA)	х		х	х	М	х	Х	х	х	X	М	х	х
Manifest Refraction	х			х	M	X	х	х	х	х	M	Х	
Best corrected Visual Acuity Distance (BCDVA)	:x			X.	M	· x ·	X	х	х	х	М	х	
In-office Erythropsia Assessment					X.	Х	x	x	x	X	x	X	х
City University Color Test					Х	X	X	х	Х	Х	х	х	X ⁵
					х	X1	X1	χ¹	$\mathbf{X_{l}}$	Χı	Xi	X ¹	
Intraocular Pressure	X		х	х	х	х	х	X	х	х	X	Х	
Slit Lamp Exam	X		X	х	X	х	х	х	Х	X.	х	x	х
Fuidus Exam	X				Х	х	х	Х	X		x	х	
Fundus Photos	х				Х	х	Х	х	х		X	Х	
					х	×	х	х	x	x	x	x	
Dilated Pupil Diameter	x				х	х	х	x	х				
						χı	X ¹	Xi	X	Xi	$\mathbf{X}_{\hat{\mathbf{I}}}$	χi	
Adverse Events		х	Х	х	х	х	x	х	х	X	X	X	Х

are only required if the events described in Section 6.4.2.2 of the protocol occur.

"Tests indicated with an "X" must be performed at each unscheduled visit. Other tests may be conducted based on the investigator's assessment of the subject.

Specular microscopy will be performed on a subgroup of approximately 300 eyes including a minimum of 192 LAL eyes and 96 Control eyes.

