If the subject reports any degree of crythropsia at the Postop Month 1-2 visit OR at any interim visit after the Postop Month 1-2 visit and <90 days after surgery, the subject will be contacted between 90-120 days after surgery and asked to complete the Daily Life Erythropsia Questionnaire.

M Measurements will be conducted by a masked observer who will not be aware of which lens has been implanted in the eye. The masked observer should not

have access to the subject's medical and/or study records.

⁵Must be performed at any unscheduled visit which occurs at 3-months or later.

Table 2. Control IOL Schedule of Visits and Clinical Parameters

1 abie 2. Control i	IOL Schedule of Visits and C				unican i	Parameters			
Visits	dosaa	Орегайче	Postop Day I	Postop Week 1	Postop Weck 3	Postop Months 1-2	Postop Month 6	Unscheduled Visit	
Demographics	х								
Ocular History	х								
History of Medications	x	X	Х	X	X	х	Х	х	
Corneal Keratometry	x								
Specular Microscopy (substudy) ²	х				X		Х		
Uncorrected distance visual acuity (UCDVA)	х		X.	X	М	x	М	-x-	
Manifest Refraction	Х			х	M	x	М		
Best corrected Visual Acuity Distance (BCDVA)	х			x	М	х	M		
Intraocular pressure	X		Х	Х	Х	X	х		
Slit Lamp Exam	Х		X	х	Х	х	Х	х	
Fundus Exam	х				Х		х		
Fundus Photos	х				X		x		
Dilated Pupil Diameter	x				х				
Adverse Events		х	Х	X	Х	Х	х	x	

Tests indicated with an "X" must be performed at each unscheduled visit. Other tests may be conducted based on the investigator's assessment of the subject. Specular microscopy will be performed on a subgroup of approximately 300 eyes including a minimum of 192 LAL eyes and 96 Control eyes, Measurements will be conducted by a masked observer who will not be aware of which lens has been implanted in the eye. The masked observer should not have access to the subject's medical and/or study records.

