7.6.3 Additional Safety Analyses

The following safety outcomes will be summarized descriptively based on the observed data and actual lens implanted. Results will be presented for all the RxSight LAL eyes and the Control group eyes. The 95% confidence intervals for means or percentage may be presented, as appropriate.

Adverse Events

Number and percent of study eyes will be summarized for each reported ocular AE at the operative visit and each postoperative visit for the LAL group and Control group separately. Serious ocular AEs and the non-ocular serious AEs will be summarized in the same manner. Additionally, for each of the device related AE reported during the study, the number and

percent of study eyes reported with the event will be presented. The ocular adverse events will be listed for eyes, if applicable, with IOL implantation attempted but without implantation. Ocular adverse events will be reported separately for the fellow eye.

BCDVA

BCDVA will be presented with the number and percent of eyes who fall into each category of BCDVA at each visit (e.g. 20/20 or better, 20/25 or better, 20/32 or better, etc.). The mean and standard deviation (SD) of BCDVA letter score will also be calculated for each visit. Change in BCDVA from Postop Week 3 or from Preoperative will be presented at each visit as categorical outcomes of "Increase in 15 letters or more", "Increase in 10-14 letters", "Increase in 5-9 letters", "No change", "Decrease in 5-9 letters", "Decrease in 10-14 letters", and "Decrease in 15 letters or more The mean and SD of the change from Postop Week 3 or Preoperative will also be presented. Similarly, the mean change from the prior visit to the next visit will also be summarized in the same manner.

In-Office Erythropsia Assessment (RxSight LAL only)

The number and percent of eyes in each outcome of erythropsia assessment (0- white, 1-pink, or 2- red) will be presented. In addition, the number and percent of eyes with increases in the level of erythropsia from the Postop Week 3 visit will be presented.

Daily Life Erythropsia Questionnaire (RxSight LAL only)

Results of the Daily Life Erythropsia Questionnaire will be summarized descriptively at each visit the questionnaire is completed.

City University Color Test (RxSight LAL only)

[figure not shown]
Results of the City University Color Test will be reported as the number and percent of eyes that have tritan findings >1 on Part Two of the test.

Slit Lamp Examinations

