Slit lamp findings will be summarized descriptively.

Fundus Exam and Fundus Photos (RxSight LAL only)

Number of subjects with fundus exam changes from the pre-op and Postop Week 3 evaluation will be summarized.

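### Section 7.6.3 restricts the fundus-change count to LAL eyes although Control eyes have the same examinations at the same visits, so the count has no matching Control figure in the visible plan

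*Combined protocol and SAP*

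**What the plan says.** The lead-in to section 7.6.3 sets a default of both arms: "Results will be presented for all the RxSight LAL eyes and the Control group eyes". Four items below it are marked LAL only: the in-office erythropsia assessment, the erythropsia questionnaire, the colour test and the fundus item, which is headed "Fundus Exam and Fundus Photos (RxSight LAL only". The whole of the fundus analysis is one sentence: "Number of subjects with fundus exam changes from the pre-op and Postop Week 3 evaluation will be summarized". It gives no percentage or denominator and does not name the visit at which a change is counted.

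The schedules are in section 6.7. "Table 2. Control IOL Schedule of Visits and Clinical Parameters" marks the fundus exam and fundus photographs at Preop, Week 3 and Month 6. "Table 1. RxSight LAL Schedule of Visits and Clinical Parameters" marks them at those three visits and also at Adjustments #2 and #3, Lock-ins #1 and #2, and Month 12 if needed. The numbered assessment list in 6.7 labels the two erythropsia measures and the colour test as LAL only; the fundus exam and photographs carry no such label.

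**The concern.** One of the study's two safety questions (section 3) is retinal damage from the light treatment. Section 8.6 lists cystoid macular edema, epiretinal membranes and other retinal problems as possible after any cataract surgery with either lens. Some fundus change is therefore to be expected in eyes that never receive light treatment, and a count in LAL eyes alone does not show how much of it is background.

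The trial has a randomised group that could supply the background, examined by the same method at the same three visits. If the visible rule is followed, those data are collected but left out of the one visible table that counts fundus changes. A reader of the LAL number could not set it beside eyes that had the same surgery and the same examination without light treatment.

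**Working it through.** The plan states no figure for this item, so there is none to reproduce. The check compares the schedules with the analysis text and then asks what a two-arm table could show.

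**1. Which LAL-only labels follow from data collection?**

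| Item marked LAL only in 7.6.3 | Scheduled in Control (Table 2)? |
|---|---|
| In-office erythropsia | No |
| Erythropsia questionnaire | No |
| City University Color Test | No |
| Fundus exam and photographs | Yes: Preop, Week 3, Month 6 |

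Three of the four restrictions are unavoidable because Control has no data. The fourth sets collected data aside.

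**2. Control data without a named summary.** Section 6 gives 500 subjects randomised 2:1, so 500 × 2/3 ≈ 333 LAL and 167 Control. At full attendance, 167 × 2 = 334 postoperative Control fundus exams (Week 3, Month 6), or 167 × 3 = 501 with Preop.

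**3. Number of examinations per eye after Week 3, up to Month 6.** Section 6.4.2 says "subjects will receive one to three adjustments and one or two lock-in treatments". The first adjustment is given at the Week 3 visit.

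- LAL minimum (1 adjustment, 1 lock-in): Lock-in #1 and Month 6 = 2.
- LAL maximum (3 adjustments, 2 lock-ins): Adjustments #2 and #3, Lock-ins #1 and #2, and Month 6 = 5.
- Control: Month 6 = 1.

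**4. Why a comparison must use shared visits.** Let q be the chance of recording a change at one exam with no device effect. Assume q is 1% to 3% (the documents give no rate) and exams are independent. The chance of at least one recorded change in k exams is 1 − (1 − q)^k.

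| q | k = 1 (Control) | k = 2 (LAL minimum) | k = 5 (LAL maximum) |
|---|---|---|---|
| 1% | 1.00% | 1.99% | 4.90% |
| 3% | 3.00% | 5.91% | 14.13% |

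An any-visit comparison would show a spurious LAL excess between 1.99 − 1.00 = 0.99 and 14.13 − 3.00 = 11.13 percentage points.

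**5. What a Month 6 table by arm could show.** For each arm with rate p, take the Wilson 95% limits (l, u). The Newcombe interval for the difference d = p₁ − p₂ (LAL minus Control) runs from d − √[(p₁ − l₁)² + (u₂ − p₂)²] to d + √[(u₁ − p₁)² + (p₂ − l₂)²].

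- 0/333 against 0/167: Wilson upper limits are 1.14% and 2.25%, so the interval is −2.25 to +1.14 points.
- 10/333 against 5/167 (3.0% each): −4.05 to +2.98.
- 24/333 against 5/167: lower limit −0.26.
- 25/333 (7.5%) against 5/167 (3.0%): +0.02 to +8.27. With 5 Control events, 25 is the smallest LAL count whose lower limit exceeds zero.
- With 10% missing (assumed; 300 and 150 eyes): 0 against 0 gives −2.50 to +1.26, and 25 against 5 gives +0.02 to +9.14.

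**6. A check before light treatment is available.** Section 6.4.2.3 says "Protocol-required measurements should be completed prior to adjustment or lock-in treatments". The Week 3 fundus exam therefore comes before any light exposure, and Week 3 against Preop by arm shows whether the arms already differ.

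**The case against.** The strongest case for leaving the plan alone has five parts.

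- **Coverage elsewhere.** Ocular adverse events are tabulated at the operative visit and "each postoperative visit for the LAL group and Control group separately", and the definitions in section 8 are wide enough to take in untoward fundus findings. Section 7.6.4 also promises both arms for all other outcomes, and its list need not be exhaustive. The adverse event point stands in part and lowers the weight. But an adverse event table counts reported events, not changes from baseline. Section 7.6.4 covers outcomes not dealt with earlier, names only acuity and refraction, and would not guarantee a count in matching form.
- **A within-eye reference exists.** Change is counted from Week 3, before light treatment, which separates out findings already present by then. It cannot separate later postsurgical change from change due to light.
- **Text that cannot be seen.** The body of 7.6.2 is not visible, and the synopsis lists rates of findings consistent with UV damage judged by an independent expert, with no arm restriction shown. The detailed SAP is still to come (section 7.2). This stands as a limit on the conclusion.
- **An imperfect comparison.** Masking covers only acuity and refraction, the analysis is by lens actually implanted, and LAL subjects with intraoperative complications before implantation are exited, while section 6.5 states no parallel rule for Control. These are fair caveats for a descriptive table, not reasons to omit the Control arm.
- **An understandable choice.** The co-primary retinal endpoint is itself defined for LAL eyes, and the lead-in to 7.6.3 is a default that a specific heading may override. That is so, and the heading is best read as an exception rather than a contradiction. No reason for the exception is visible.

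**Conclusion.** The concern holds, with minor to moderate weight. A stated rule in 7.6.3 excludes scheduled, randomised Control fundus data (about 334 postoperative exams at full attendance) from the one visible table of fundus changes, on a subject close to one of the study's two questions. The gap is narrow: the LAL change count has no matching Control count.

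No primary endpoint, sample size or error rate is affected. The rate of fundus changes that would not reach the adverse event tables is not given and is not estimated here. A two-arm table could bound or reveal only a large difference: at best about −2.2 to +1.1 points when neither arm shows a change. The 1.0 to 11.1 point artefact rests on the assumed 1% to 3% per-exam rate and independence, and its top end requires every LAL eye to have all five exams. It describes an any-visit comparison that the plan does not propose, and it matters only for how the table should be built. The conclusion is limited to the visible text.

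**What to change.** In section 7.6.3, remove the LAL-only restriction from the fundus heading and specify in the SAP:

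- number and percent of eyes with a fundus change, with denominators, by arm, at the shared visits only: Week 3 against Preop, Month 6 against Preop, and Month 6 against Week 3;
- a label stating that the table is descriptive, with 95% confidence intervals optional, as 7.6.3 already allows;
- a separate LAL-only table for findings at the adjustment and lock-in visits, so that the extra examinations do not enter the comparison;
- a footnote that the analysis is by lens implanted and that no masked fundus assessment is described, unless the SAP adds one.

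If the SAP keeps the restriction, it should state why Control is left out.

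The cost is one heading edit and one more column in a descriptive table. Table 2 already schedules the data; no visit, test or sample size changes.

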7.6.4 Additional Analyses

All other clinical outcomes will be summarized descriptively at each visit based on the observed data and actual lens implanted. Results will be presented for all the RxSight LAL eyes and the Control group eyes. The 95% confidence intervals for means or percentage may be presented, as appropriate. These clinical outcomes include uncorrected visual acuity (UCVA), manifest cylinder (MRCYL), manifest spherical equivalent (MRSE), absolute MRSE, MRCYL or MRSE within 0.50 D and 1.00 D from intended correction, change in MRCYL or MRSE or absolute MRSE from Postop Week 3, vector change in MRCYL from Postop Week 3, and Defocus Equivalent (DEQ). Additionally, the stability of MRSE and MRCYL will be summarized per Section F.3 of ANSI Z80.11-2012.

8 ADVERSE EVENTS

Throughout the course of the study, all efforts will be made to remain alert to possible adverse experiences or untoward findings. If adverse events occur, the first concern will be the safety and welfare of the subject and appropriate medical intervention will be made. All anticipated and unanticipated adverse events regardless of severity will be captured on the Case Report Forms (CRF) and the Adverse Event Form.

All adverse events will be evaluated by the manufacturer/study sponsor (RxSight) per the internal procedure (OP 1026) to determine if the event is reportable to FDA under 21 CFR § 803: Medical Device Reporting, Subpart E – Manufacturer Reporting Requirements. Study events meeting the definition below of an MDR reportable event will be reported to CDRH electronically via the eMDR system within the required time frames. In addition, the post approval study reports shall include a summary table of MDRs filed for this PAS study.

8.1 ADVERSE EVENT DEFINITIONS

An adverse event (AE) is any untoward medical occurrence, unintended disease or injury, or untoward clinical signs (including abnormal laboratory findings) in subjects, users, or other persons, whether or not related to the investigational medical device.

Note 1 to entry: This definition includes events related to the investigational medical device or the comparator.

Note 2 to entry: This definition includes events related to the procedures involved.

Serious Adverse Events (SAEs) are AEs that lead to:

- death
- a serious deterioration in the health of the subject that:
 - results in a life-threatening illness or injury
 - results in a permanent impairment of a body structure or function (e.g., blindness)
 - requires in-subject hospitalization or prolongation of existing hospitalization
 - results in medical or surgical intervention to prevent permanent impairment to a body structure or a body function
- fetal distress, fetal death, or a congenital abnormality or birth defect
- a potentially sight-threatening condition
- or is another important medical event.

MDR reportable event: An event that manufacturers become aware of that reasonably suggests that one of their marketed devices:

- · May have caused or contributed to a death or serious injury, or
- Has malfunctioned and that the device or a similar device marketed by the manufacturer or importer would be likely to cause or contribute to a death or serious injury if the malfunction were to recur.

Serious injury means an injury or illness that:

- · Is life-threatening,
- Results in permanent impairment of a body function or permanent damage to a body structure, or
- Necessitates medical or surgical intervention to preclude permanent impairment of a body function or permanent damage to a body structure. Permanent means irreversible impairment or damage to a body structure or function, excluding trivial impairment or damage.

The following may be considered normal events after cataract surgery and only need to be reported as AEs as specified:

- Iritis/cells/flare (if present after Postop Week 1 and greater than grade 1 (trace)) or (any iritis/cells/flare present at Postop Month 6 of any grade)
- Chronic anterior uveitis-anterior segment inflammation characterized by grade 1+ cell or greater (using the Standardization of Uveitis Nomenclature criteria) that is persistent for greater than 3 months postoperatively, or relapses in less than 3 months after discontinuation of therapy, or the subject is maintained on therapy for more than 3 months to control inflammation
- Corneal edema (corneal swelling (stromal or epithelial) (if present after Postop Week 1 and greater than grade 1 (trace)), OR resulting in BCDVA of 20/40 or worse at Postop Month 1-2 or later, OR (if present at Postop Month 6 of any grade)
- Raised intraocular pressure (IOP) >10 mmHg above preoperative and greater than 25 mmHg (if present after Postop Week 1) AND unrelated to mechanical pupillary block

In addition, the specific following events should be reported as an AE:

- An increase in score of more than 1 on Part 2 of the Tritan evaluation (City University Color Test) when compared to the Postop Week 3 score.
- An erythropsia score of 2 (red) at any time after Postop Week 3.
- An eythropsia score of 1 (pink) or (2) red at the Postop Month 6 visit.

All adverse events should be reported and information provided regarding whether the adverse event meets the above definitions.

8.2 IDENTIFICATION AND COLLECTION

Identification and collection of an AE begins after informed consent has been obtained and documented. Standard sources of identifying AEs include:

- direct observation by the Investigator or study team member
- asking the study participant a specific question (e.g., "Since your last visit, have you experienced any problems with your eyes or vision?")
- unsolicited volunteering of information by the study participant (e.g., "Doctor, I have had numerous headaches since I started using this lens.")

Ocular AEs and SAEs and systemic SAEs observed or elicited by the Investigator, reported by the subject, or resulting from a test result, etc., occurring during the clinical investigation must be documented. During the study, the Investigator should treat the study subject as appropriate to ensure his/her safety and welfare. Refer to Section 6.9.1 for additional information pertaining to ongoing AEs at subject exit.

Pre-existing conditions will not be considered AE/SAEs but will be collected at the Preoperative Visit as medical history. A worsening of a pre-existing condition during the study should be documented as an AE and evaluated accordingly.

Hospitalization is a criterion for assessment of seriousness. Hospitalization in the absence of a medical AE is not in itself an AE. For example, the following reports of hospitalization without a medical AE should not be considered either an SAE or an AE:

- Planned hospitalization for a pre-existing condition without serious deterioration in health (e.g., planned knee replacement surgery)
- Social admission (e.g., subject has no place to sleep)
- Administrative admission (e.g., for yearly physical exam or elective procedures not related to the study)
- Optional admission not associated with a precipitation medical AE (e.g., for elective cosmetic surgery)

